15.4.2 Skin Irritation Data**15.4.2.1 Source Data**

The source data are the erythema, edema, rash, and dryness scores assigned on the test day by the technician immediately before samples are taken at baseline and at 10 minutes and 6 hours after treatment application. The data to be used in the statistical analysis of irritation are the changes from baseline. These data will be sent to the microbiology laboratory site and separate analyses will be conducted for each irritation parameter.

15.4.2.2 Within-Treatment Analysis

Wilcoxon's Signed Rank Test will be used to evaluate changes from baseline at each post treatment evaluation.

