10.0 SUBJECT SELECTION

10.1 Number of Subjects

The requirement of 111 subjects per test article configuration (test arm) to finish this study was determined by the sample size equation at the recommendation of both the FDA Proposed Rule and ASTM E1173; the following formula was used for group size calculations:

$$n \geq s^2 \frac{(Z_{\alpha/2} + Z_{\beta})^2}{\Delta^2}$$

Where:

- n = minimum number of required samples in each test arm (rounded up).
- s = standard deviation of the acquired data (0.735).
- $Z_{\alpha/2}$ = the Z statistic for a two-sided 95% confidence interval (1.96), where α (0.05) is the probability of allowing a Type I error (predicting significance when there is none).
- Z_{β} = the Z statistic for the power of the test (0.842), where β (0.80) is the power, i.e., the probability of allowing a Type II error (failing to predict significance when it exists).
- Δ = the difference being tested for (0.196).

The best reasonable estimate of the number of subjects needed per test article configuration (study arm), based on available current data is 111.

Since there are five study arms, the minimum number of subjects based on bilateral applications is 278 (Five arms x 111 / 2).

Initial screening baseline counts will be collected from a number of healthy subjects of at least the age of sixteen sufficient to provide at least 278 qualified subjects to enter the treatment phase of the study. (NOTE: As it is anticipated that not all subjects that have qualifying screening-day baseline counts will have qualifying test-day baseline counts, it may be necessary to treat more than 278 subjects.)

The eligibility of each subject will be determined from a medical history collected on the Screening Inclusion/Exclusion Form and Treatment Inclusion/Exclusion Form (to be provided prior to study initiation).

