14.0 ASSESSMENT OF SAFETY

14.1 Skin Irritation

The safety of each test product will be evaluated by observing irritation before samples are taken at baseline and at 10 minutes \pm 30 seconds and 6 hours \pm 30 minutes after completion of prep.

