14.2.4 Anticipated Reactions

The risks associated with this test are primarily related to application of the test article. Tape reactions are also possible. Mild to heavy erythema, swelling, itching, cracking, peeling, or in rare cases, blistering and or an allergic reaction might occur.

Occurrence of any of these events will be considered an "Adverse Event" and will be documented in the study record.

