15.0 DATA AND STATISTICAL ANALYSIS

The analyses outlined below will be conducted on the data generated.

- 15.1 Raw data (CFU/mL) will be converted to \log_{10} CFU/cm². Counts of less than 1 CFU /cm² will be treated as 1 CFU/cm² such that the log transformation will be zero. Log reductions will be calculated by subtracting the post treatment log counts from the treatment day baseline counts obtained.
- 15.2 Only subjects who meet the minimum inclusion criteria for levels of bacteria on the treatment day of the study will be included in the analysis with the following exception: lab accidents resulting in contaminated samples. If there are missing data at some but not all time points, data from the available times will be included in the analysis.
- 15.3 Any subject with missing data will not be included in the data analysis. The subject with missing data will be replaced with a new subject.
- 15.4 Separate statistical analyses will be conducted for data collected from the abdomen and the groin. All hypothesis testing will be conducted at the alpha=0.05 level of significance. Data will be presented in tabular and graphical format.

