15.4.1.3 Within-Treatment Analysis

- The average combined screening baseline and treatment day baseline \log_{10} CFU will be compared to the \log_{10} CFU at the 10-minute and 6-hour post treatment evaluations utilizing Student's t-test for paired data.
- The \log_{10} CFU at the treatment day baseline will be compared to the \log_{10} CFU at the 10-minute and 6-hour post treatment evaluations utilizing Student's t-test for paired data.

Summary statistics will consist of mean \log_{10} CFU (\pm 95% CI) and mean \log_{10} CFU differences (\pm 95% CI) expressed as geometric mean \log_{10} reductions.

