15.4.2.3 Between-Treatment Analysis

The changes from baseline will be averaged across the 10-minute and 6-hour evaluation times. The Kruskal-Wallis test will be used to compare the irritation levels of the test products.

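### Skin irritation is analysed by rank tests alone: section 15.4.2 should add the proportion of sites that worsen, with exact 95% limits, because a non-significant test does not bound the reaction rate (minor)

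*Combined protocol and SAP*

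**What the plan says.** Section 14.1 states: "The safety of each test product will be evaluated by observing irritation before samples are taken at baseline", and again at 10 minutes and 6 hours. Section 15.4.2.1 names four scored parameters (erythema, edema, rash and dryness), each analysed separately as change from baseline.

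Two analyses follow. Section 15.4.2.2: "Wilcoxon's Signed Rank Test will be used to evaluate changes from baseline at each post treatment evaluation". Section 15.4.2.3, on the change averaged over the two times: "The Kruskal-Wallis test will be used to compare the irritation levels of the test products". Section 15.4 adds "All hypothesis testing will be conducted at the alpha=0.05 level of significance" and separates abdomen from groin. It promises tables and graphs without specifying their content.

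For the microbial data, section 15.4.1.3 plans means and mean differences with 95% confidence intervals. Section 15.4.2 has no counterpart: no incidence, interval, upper bound or acceptable irritation limit.

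Section 14.2.4 makes skin reactions adverse events, and section 14.2.1 grades them for severity and causality. No incidence summary of adverse events is specified. Of the worst reactions, section 14.2.4 says "in rare cases, blistering and or an allergic reaction might occur".

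**The concern.** Subjects must have skin near the test sites free of dermatoses and lesions (10.2.4), and the sites are examined again on the test day (12.3.1). Most baseline scores should therefore be at or near zero, and most changes zero. In such data a rank test responds to common shifts and has little to work with when only a few sites worsen.

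A p-value above 0.05 is then compatible with a reaction rate of several percent, and nothing specified in 15.4.2 tells the reader how large that rate could be. The risk is that the report treats a non-significant test as reassurance about irritation when the data support only a bound, and the plan does not ask for that bound.

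**Working it through.** **Inputs.** Section 10.1: "The best reasonable estimate of the number of subjects needed per test article configuration (study arm), based on available current data is 111". Section 6.0 gives 111 evaluations per arm in each region. Alpha is 0.05 (15.4). The plan's figure reproduces: 0.735² × (1.96 + 0.842)² / 0.196² = 110.41, rounded up to 111.

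**Assumptions.** The documents give no irritation rate and no scoring scale. I take baseline scores as 0, count any increase as a reaction, and assume no site improves. Each calculation is for one region, one parameter and one time point.

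**Signed-rank test, exact, two-sided, zeros dropped.** With k worsened sites, the smallest possible p is 2 × 0.5^k:
- k = 5: 0.0625
- k = 6: 0.031

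So 5 of 111 (4.5%) is the largest count that cannot reach 0.05.

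**Other versions.** With k equal changes, the tie-corrected normal approximation gives z = [k(k+1)/4] / √[k(k+1)(2k+1)/24 − (k³−k)/48] = √k.
- k = 3: p = 0.083. k = 4: z = 5/2.5 = 2, p = 0.0455. The ceiling is 3 of 111 (2.7%).
- With continuity correction, k = 4: z = 4.5/2.5 = 1.8, p = 0.072; k = 5: p = 0.037. The ceiling is 4 of 111 (3.6%).
- Exact one-sided, k = 4: 0.0625; k = 5: 0.031. The ceiling is again 4.

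**What those counts allow.** The Clopper-Pearson two-sided 95% upper limit is the 0.975 quantile of Beta(x+1, 111−x):

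| Worsened sites | Observed | Upper limit |
|---|---|---|
| 0/111 | 0% | 3.3% |
| 3/111 | 2.7% | 7.7% |
| 5/111 | 4.5% | 10.2% |

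**Chance that the within-article test misses a true rate p.** This is P(Bin(111, p) ≤ ceiling):

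| True rate | Ceiling 5 (exact) | Ceiling 3 (approximation) |
|---|---|---|
| 3% | 88% | 57% |
| 4% | 72% | 35% |
| 5% | 52% | 19% |

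**Kruskal-Wallis.** I treat the score as reaction or no reaction, and take five independent arms of 111. The statistic is then the Pearson chi-square × (N−1)/N with N = 555, on 4 df (5% critical value 9.49).
- 5/0/0/0/0 reactors: mean 1 per arm, squared deviations 16 + 4×1 = 20; 20/[1 × (1 − 5/555)] × 554/555 = 20.15, p = 0.0005.
- 5/5/0/0/0: p = 0.004.
- 5/5/1/1/1: mean 2.6, squared deviations 2×5.76 + 3×2.56 = 19.2; 19.2/[2.6 × (1 − 13/555)] × 554/555 = 7.55, p = 0.11.
- 5/5/5/1/1: mean 3.4, squared deviations 3×2.56 + 2×5.76 = 19.2; 19.2/[3.4 × (1 − 17/555)] × 554/555 = 5.82, p = 0.21.

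The last pattern is plausible, because both ChloraPrep arms and Hibiclens contain chlorhexidine (section 7.0).

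**Both tests together.** Simulated for true rates in the two ChloraPrep arms against the other three, the chance that Kruskal-Wallis or the exact signed-rank test in either ChloraPrep arm is significant is:
- 3% against 1%: about 28%
- 5% against 1%: 77%
- 6% against 2%: 89%
- 10% against 5%: 99.9%

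The first figure depends on the test version. At a true rate of 3%, the signed-rank test alone flags at least one ChloraPrep arm with probability 1 − 0.882² = 22% if exact, and 1 − 0.573² = 67% under the approximation with ceiling 3.

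**The case against.** The strongest reply has four parts.

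- **The ceiling is not a property of the plan.** Neither the version of the signed-rank test nor its handling of zeros and ties is stated. Two-sidedness appears only in the sample-size section ("the Z statistic for a two-sided 95% confidence interval (1.96"). This stands. A reader might infer that 5 of 111 sites can react undetected; the documents support only a ceiling of 3 to 5, depending on the version.
- **Kruskal-Wallis is a backstop.** This stands in part. A reader might infer that a product irritating a few percent of sites would pass both tests. With 5 reactors in one arm and none elsewhere Kruskal-Wallis gives p = 0.0005, and at 5% or more in both ChloraPrep arms the two tests together usually flag something. The backstop is weak when there are background reactions and low rates, or when several arms share the rate.
- **Skin reactions are captured elsewhere.** This stands as to recording. It would be wrong to say that safety rests on rank tests alone, or that the severity of a blister is lost in the ranks. Blistering is not one of the four scored parameters; it is a documented, graded adverse event notified to the sponsor (14.2.1, 14.2.3, 14.2.4). Counts will exist, but no rate, limit or comparison is planned for them.
- **The plan never equates p > 0.05 with non-irritating**, and its stated aims concern antimicrobial effect. This is true, and it keeps the point minor. Section 14.1 still makes irritation the safety evaluation, and 15.4.2 supplies only p-values for it.

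**Conclusion.** The concern holds as a cheap improvement of minor severity. Section 15.4.2 specifies tests but no estimate, and with mostly zero changes a non-significant test does not limit the reaction rate. Depending on the unstated version of the signed-rank test, 3 to 5 worsened sites of 111 cannot reach 0.05, while the true rate could be as high as 7.7% (3/111) or 10.2% (5/111). The gap is confined to low rates and to rates shared across arms; the planned tests would usually detect clear excesses in the ChloraPrep arms.

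This rests on near-zero baseline scores, no improvements, scores reduced to reaction or no reaction, and arms treated as independent although each subject carries two articles. The further time point, parameters and region give additional chances of a significant result, which the figures above leave out. None of those results would supply a bound.

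**What to change.** In section 15.4.2, for each arm, region, parameter and time point, add:

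1. The number and percentage of sites with any increase from baseline, and by worst grade, with exact (Clopper-Pearson) 95% limits.
2. The difference in that percentage, ChloraPrep minus the water arm with the same application procedure and ChloraPrep minus Hibiclens, with 95% confidence intervals.

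Base the irritation statement on these and keep the two rank tests as support. State the version of the signed-rank test, its sidedness, and how zeros and ties are handled. Say that a non-significant test will not be reported as evidence of no irritation; with 0 of 111 worsened sites, the supportable statement is a rate below 3.3%.

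The cost is a few sentences and one extra table of 5 arms × 2 regions × 4 parameters × 2 times = 80 rows, from scores already collected. No subjects or procedures are added. The downside is a less absolute safety statement: a rate below a stated bound in place of no significant irritation.

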15.4.2.3 Between-Treatment Analysis

The changes from baseline will be averaged across the 10-minute and 6-hour evaluation times. The Kruskal-Wallis test will be used to compare the irritation levels of the test products.

16.0 SPECIAL NOTES**16.1 Informed Consent**

A written consent form from each subject will be obtained and filed by the Investigator with the subject's records, in accordance with 21 CFR 50 & 56.

16.2 Alteration of the Study

Neither the Investigators nor the Sponsor will modify or alter this protocol without first obtaining the concurrence of the other parties. Approval of the modification by the Investigators' IRB must be obtained before implementation, with two exceptions:

- a. When necessary to eliminate an apparent immediate hazard to the subject.
- b. When modification does not involve the subject's participation in the study.

17.0 REPORT

The final report will summarize the method, data and conclusions relative to the test materials and the subjects.

18.0 NOTICE

No amendments to the protocol will be permitted without approval from the Study Sponsor, the Investigators, and the Institutional Review Boards. Such changes will be documented in writing. Approval by the Board must be obtained prior to initiation of the amendment.

	 Present before study  Symptoms of primary disease  Concomitant Medications  Intercurrent illness  Intercurrent event  Other (Comment below)	 Nature  Severity	 Recovered Date: Mo. 

 	 	

 Day 

 	 	 	

 Year 

 	 	 	

								
 Not Related  Not Serious  Serious (life threatening or results in death, permanently disabling, requires inpatient hospitalization, a congenital anomaly, cancer or overdose)	 Other (Comment below)	 Persistent Effect (Describe below)  Death (Describe below)									

Identify Study Drug involved in the Adverse Event:

Describe the Adverse drug experience; provide chronology of events, actions taken and outcome. Use another form if needed.

*Did the adverse experience increase in severity? Yes No
 If yes, to what degree? Moderate Severe

Investigator Signature:	Date:
-------------------------	-------

APPENDIX 1**TEST ARTICLE PREPPING TECHNIQUES****A. Test Product: ChloraPrep Triple Swabsticks****1. Application Configuration No. 1 (Three swabsticks applied all at once)****On Abdomen:**

- a. All three swabsticks will be applied to the surface of the treatment area with the flat side down.
- b. Using all of the three swabsticks together, the solution will be applied within the designated treatment area using repeated back and forth applications of the sponge for 30 seconds so that a thin even coat is applied.
- c. The area will be allowed to air-dry based on visual observations for approximately 30 seconds prior to the initiation of the contact times. The test article exhibit glistening wet shine after application and dry time will be documented, as wet shine will disappear leaving a faint visible film. The patient specific dry time observed will be documented and reported.

On Groin:

- a. All three swabsticks will be applied to the surface of the treatment area with the flat side down.
- b. Using all of the three swabsticks together, the solution will be applied within the designated treatment area using repeated back and forth applications of the sponge for two minutes so that a thin even coat is applied.
- c. The area will be allowed to air-dry based on visual observations for approximately one minute prior to the initiation of the contact times. The test article exhibit glistening wet shine after application and dry time will be documented, as wet shine will disappear leaving a faint visible film. The patient specific dry time observed will be documented and reported.

APPENDIX 1 (continued)**TEST ARTICLE PREPPING TECHNIQUES (continued)****A. Test Product: ChloraPrep Triple Swabsticks (continued)****2. Application Configuration No. 2 (Three swabsticks applied sequentially)****On Abdomen:**

- a. Each swabstick will be applied to the surface of the treatment area with the flat side down.
- b. Using one of the three swabsticks, the solution will be applied within the designated treatment area using repeated back and forth applications of the sponge for approximately 10 seconds so that a thin even coat is applied.
- c. The same procedure will be repeated using the second and third swabstick for a total application time of approximately 30 seconds.
- d. The area will be allowed to air-dry based on visual observations for approximately 30 seconds prior to the initiation of the contact times. The test article exhibit glistening wet shine after application and dry time will be documented, as wet shine will disappear leaving a faint visible film. The patient specific dry time observed will be documented and reported.

On Groin:

- a. Each swabstick will be applied to the surface of the treatment area with the flat side down.
- b. Using one of the three swabsticks, the solution will be applied within the designated treatment area using repeated back and forth applications of the sponge for approximately 40 seconds so that a thin even coat is applied.
- c. The same procedure will be repeated using the second and third swabstick for a total application time of approximately two minutes.
- d. The area will be allowed to air-dry based on visual observations for approximately one minute prior to the initiation of the contact times. The test article exhibit glistening wet shine after application and dry time will be documented, as wet shine will disappear leaving a faint visible film. The specific dry time observed will be documented and reported.

APPENDIX 1 (continued)**TEST ARTICLE PREPPING TECHNIQUES (continued)****B. Reference Control: Hibiclens**On Abdomen and Groin

1. Based on the manufacturer's instructions, five mL of the reference product will be applied onto a sterile gauze pad.
2. The product will be applied to the treatment area using the same area used for the test product for two minutes. The area will be dried with a sterile towel or sterile gauze.
3. Steps 1-2 will be repeated.
4. Contact times will begin after the site has dried a second time.

C. Negative Control: Sterile Swabsticks with Sterile Deionized Water

For both application configurations (No. 1 and No. 2 outlined in Part A), three sterile swabsticks will be placed into a sterile tube containing 5.25 mL of sterile deionized water for 10 seconds before application.

On Abdomen and Groin:

The application procedures and application variations will be the same as used for Chloraprep Triple Swabsticks (Part A).

APPENDIX 2

NEUTRALIZER VALIDATION PROCEDURE

1.0 OBJECTIVE

The objective of this evaluation is to determine the ability of the sampling solutions to completely neutralize the active ingredients contained in the test and positive control products applied to the abdomen of test subjects without exhibiting toxicity to the marker organism.

2.0 SUBJECT ENTRY CRITERIA

Six subjects will participate in this study to yield six readings per test article, including both application configurations for the ChloraPrep Triple Swabsticks whereas three sites will be delineated on the abdomen, two for the ChloraPrep Triple Swabsticks and one for Hibiclen. Subjects must meet the inclusion and exclusion criteria in Sections 10.0 of the protocol to which this neutralizer validation is to be performed. The neutralization subjects do not require a minimum bacterial count, but they still need to avoid topical and systemic antimicrobials for 14 days prior to the treatment day. Each subject will receive both of the test articles, one product per side.

3.0 TEST ARTICLES

- 3.1 ChloraPrep Triple Swabsticks
- 3.2 Hibiclen

4.0 TEST ORGANISM

Staphylococcus epidermidis ATCC 12228. The test organism from the frozen stock culture will be transferred into 10 mL of Tryptic Soy Broth and incubated at 30±2 C. After 24 hours of incubation this culture will be diluted into ten fold dilutions using Butterfield's Phosphate Buffered Dilution water to achieve an appropriate concentration for inoculation of the test samples.

5.0 PROCEDURE [NOTE: All testing described in this section will be performed in triplicate.]

- 5.1 Serially dilute the overnight suspension with Butterfield's phosphate buffered water (PBW) to achieve an appropriate concentration for inoculation of the test samples.

Note: The density of the test inoculum must be verified by direct plating at beginning and end of this evaluation.

5.2 **Neutralization Effectiveness Control:** Samples will be taken from the abdomen with scrub solution containing neutralizers. The subject number, location of the prep application, location of the sites sampled within the prep area, and the time of sample collection will be documented on the CRF.

5.2.1 Mark the abdominal test areas using a sterile 2" x 5" template (three sites total).

5.2.2 After the test areas are marked, prep each site with three 70% isopropyl alcohol swabs for a total of one minute and wait site to dry.

5.2.3 Prep the each site with one of the two test articles according to randomization scheme per Appendix 1 (whereas two sites will be used for ChloraPrep Triple Swabsticks, each of which will be used for one of the two application configurations).

5.2.4 Using the cup scrub technique, at 10 minute post prep collect the sample using scrub solution containing neutralizers.

5.2.5 Each pooled sample (approximately 6 mL) will be mixed on a Vortex-type mixer and immediately inoculate this tube with approximately 30-100 CFU per mL.

5.2.6 Immediately (< one minute) and at 30 minutes (\pm 2 minutes) post-inoculation, pour-plate duplicate 1.0 mL aliquots of the inoculated sample using TSA containing neutralizers. Incubate the plates at 30 \pm 2C for 72 \pm 4 hours.

5.3 **Number Controls:** Add diluted inoculum into a tube containing 6.0 mL of sampling solution without neutralizers yield final inoculum concentrations of ~30-100 CFU/mL. Plate duplicate 1.0 mL aliquots immediately (< 1 minute) and 30 minutes (\pm 2 minutes) post inoculation in the same manner as 5.2.6 above except using TSA without neutralizers.

5.4 **Toxicity Control:** Add diluted inoculum into a tube containing 6.0 mL of sampling solution containing neutralizers yield final inoculum concentrations of ~30-100CFU/mL. Plate duplicate 1.0 mL aliquots immediately (< 1 minute) and 30 minutes (\pm 2 minutes) post inoculation in the same manner as 5.2.6 above.

These controls will provide assurance that the test organism is not adversely affected by the sampling solutions or procedure.

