9.0 NEUTRALIZATION

The objective of this evaluation is to determine the ability of the sampling solutions to completely neutralize the active ingredients contained in the test products and positive control when applied to the abdomen of test subjects without exhibiting toxicity to the marker organism. The test microorganism used for the neutralization study will be *Staphylococcus epidermidis*, ATCC 12228, a common skin bacterium. The procedure to be used is shown in Appendix 2.

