5.7 Data Evaluation

Recovery for each of the samples will be expressed as Log_{10} CFU/mL.

Neutralizer Effectiveness: If the Log_{10} CFU/mL of the antiseptic sample is not more than 0.3 logs less than the Numbers Control, the neutralizer will be considered effective.

Neutralizer Toxicity: If the Toxicity Control (TC) is not more than 0.3 logs less than the Numbers Control sample, the sampling solutions will be considered non-toxic.

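### The neutralizer validation never reproduces the groin application of ChloraPrep, and the plan does not say why the abdominal condition it uses can stand in for it

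*Combined protocol and SAP*

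**What the plan says.** Section 9.0 sets the aim: the sampling solutions must be shown to "completely neutralize the active ingredients contained in the test products and positive control when applied to the abdomen of test subjects". Appendix 2, 1.0 repeats that aim with the same restriction to the abdomen. Appendix 2, 5.2 confirms the site: "Samples will be taken from the abdomen with scrub solution containing neutralizers". Appendix 2, 2.0 gives the layout for each of six subjects: "three sites will be delineated on the abdomen, two for the ChloraPrep Triple Swabsticks and one for Hibiclen". Step 5.2.1 marks each site with a 2 x 5 in template, and step 5.2.3 says "Prep the each site with one of the two test articles according to randomization scheme per Appendix 1".

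Appendix 1 has two ChloraPrep procedures for each configuration. With the three swabsticks held together, the abdomen is prepped "using repeated back and forth applications of the sponge for 30 seconds so that a thin even coat is applied" and then dried for about 30 seconds. The groin is prepped "using repeated back and forth applications of the sponge for two minutes so that a thin even coat is applied" and dried for about one minute. The sequential configuration has the same totals. Hibiclens has a single procedure covering both regions: two minutes, dry, then repeat.

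Section 12.3.4 sets the trial's treatment areas at 2 x 5 in for the groin and 5 x 5 in for the abdomen. Under Appendix 2, 5.7, if the recovery from the antiseptic sample "is not more than 0.3 logs less than the Numbers Control, the neutralizer will be considered effective".

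**The concern.** A neutralizer validation supports the trial's counts only for the residues it has been challenged with. The ChloraPrep condition in Appendix 2 matches neither trial site: it takes the groin's area and, as most readers would understand it, the abdomen's application and drying times. No validation sample receives the groin application, and no bridging argument is given.

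The groin supplies half of the planned evaluations (111 of 222 per arm, Section 6.0) and carries the stricter criterion, 3.0 log10 at 10 minutes against 2.0 on the abdomen (Section 12.2.2). If a groin sample held more residue than the solution can neutralize, organisms would die after collection and be counted as killed on the skin. Baselines are taken before prepping and the water arms contain no antiseptic, so neither would share the loss. Hibiclens is validated with its groin procedure on the groin area. The gap is therefore confined to ChloraPrep, and any resulting error would flatter the test product.

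**Working it through.** **Step 1. Reproduce the plan's own totals.** Sequential configuration, Appendix 1: abdomen 3 x 10 s = 30 s; groin 3 x 40 s = 120 s. Both agree with the totals the appendix states and with the times for the all-at-once configuration.

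**Step 2. Set the ChloraPrep conditions side by side.** The validation column assumes that step 5.2.3 points to the abdomen procedure.

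| | Validation (App. 2) | Trial groin | Trial abdomen |
|---|---|---|---|
| Area | 2 x 5 = 10 sq in | 2 x 5 = 10 sq in | 5 x 5 = 25 sq in |
| Swabsticks | 3 | 3 | 3 |
| Application | about 30 s | about 120 s | about 30 s |
| Drying | about 30 s | about 60 s | about 30 s |
| Swabsticks per sq in | 3/10 = 0.30 | 3/10 = 0.30 | 3/25 = 0.12 |
| Seconds per sq in | 30/10 = 3.0 | 120/10 = 12.0 | 30/25 = 1.2 |

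**Step 3. Ratios.**
- Application time, groin to validation: 120/30 = 4, for both configurations.
- Drying time, groin to validation: 60/30 = 2.
- Nominal product per area, groin to validation: 0.30/0.30 = 1.
- Nominal product per area, validation to trial abdomen: 0.30/0.12 = 2.5.
- Hibiclens application time, groin to validation: (2 x 2 min)/(2 x 2 min) = 1, on the same 10 sq in.

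The validation is thus more demanding than the trial abdomen in product per area. Against the groin it is equal in product per area and shorter in working time.

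**Step 4. How a loss would enter the analysis.** Let L be the log10 loss between sampling and counting. The recorded post-treatment count is the true log count minus L, so the log reduction in Section 15.1 becomes the true reduction plus L, down to the floor of 1 CFU/cm². Because the Section 15.4.1.4 covariates are measured before prepping, they do not absorb L. It passes directly into the groin contrast of ChloraPrep with Hibiclens or water. The documents give no value for L, and none is assumed here.

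**Step 5. Where on the count scale this matters.** A groin site at the minimum baseline of 10^5 CFU/cm² with exactly a 3.0 log10 reduction is left with 100 CFU/cm². With a 3.8 cm² cup and 6 mL of fluid (Section 12.4.2), that is 100 x 3.8 / 6 = 63 CFU/mL, inside the 30-100 CFU/mL range used to spike the validation samples. Such a sample can be counted with little or no dilution, so dilution would do little to weaken any residue.

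**The case against.** The strongest reply is that a neutralizer is challenged by the antiseptic under the cup, not by rubbing time. The validation uses the same three swabsticks, in the same two configurations, on the same area as the groin. Both procedures aim at a thin coat and allow drying before timing starts, and nothing in the documents shows that longer rubbing leaves more residue. This stands in part. A reader might infer a 4-fold shortfall in antiseptic load; Step 3 shows that the factor of 4 applies to application time only. What remains is that four times the working time, on different skin, could change how much product is released and retained, and the plan neither tests nor discusses it.

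Four further replies have weight:

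- **The hold is tested.** A reader might infer that killing during the wait before plating goes unexamined. Appendix 2, 5.2.6 plates within one minute and again at 30 minutes, matching the 30-minute plating limit in Section 12.4.2. The diluent and the plating agar also contain neutralizers. These are real safeguards, but their adequacy is shown only for the residue actually tested.
- **Hibiclens challenges the same solution.** It is 4% CHG, applied twice, against 2% in ChloraPrep. This is partial reassurance: Hibiclens is dried with a towel or gauze, ChloraPrep is left to air-dry, and ChloraPrep also contains 70% isopropyl alcohol.
- **The 30 seconds is inferred.** Appendix 2 states no duration. If the groin procedure was intended, the defect is one of wording, but the text still has to say so.
- **The solution's spare capacity cannot be judged.** The scrub solution's composition is redacted in the public copy. That is not a fault in the plan, and it means neither adequacy nor inadequacy can be argued from the formula.

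**Conclusion.** The point holds as an unbridged gap in a laboratory control. No planned validation sample reproduces the groin ChloraPrep application. The difference is 4-fold in application time and 2-fold in drying time, with nominal product per area equal. Any carry-over missed for this reason would act in one direction, in favour of ChloraPrep in the groin.

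This rests on two assumptions: that step 5.2.3 refers to the abdomen procedure, and that longer working could leave more residue in the cup. The documents do not contradict the first and are silent on the second.

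Two stronger readings are not supported. One is that carry-over occurs in the groin, or that the ChloraPrep groin results will be biased; the documents neither show this nor size it. The other compares the 0.3 log10 acceptance limit with the 0.196 log10 difference used for sample size and concludes that there is no room for error. The 0.3 is a maximum pass limit for a spiked control and applies equally to both products, and 0.196 is a planning figure. The comparison says nothing about groin against abdomen.

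The change is worth making because it is cheap and because killing in the tube cannot be separated from killing on the skin once the groin data have been collected.

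**What to change.** Reconcile Appendix 2 (1.0, 5.2.1 and 5.2.3) and Section 9.0 with Section 12.3.4 and Appendix 1:

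- State in 5.2.3 which Appendix 1 procedure applies to the validation sites. For both ChloraPrep configurations, the sampling solution should be challenged with the most demanding combination of area and application that the trial already specifies.
- Amend the objectives in Section 9.0 and Appendix 2, 1.0 to say that the validation is meant to support both the abdominal and the groin counts.
- State that groin skin itself is not sampled, that the abdominal site is a bridging condition, and why it is considered adequate.

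The trial's own application procedures do not change. The validation keeps the same six subjects, three sites per subject and plates. The cost is a few sentences and slightly longer prepping of the validation sites: at most 120 - 30 = 90 s more application and about 60 - 30 = 30 s more drying per ChloraPrep site on the present figures. Some added irritation in those subjects is possible, and the validation becomes somewhat harder to pass. It should be settled before groin samples are collected.
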